## 6.2.14. Safety Analyses

Safety analyses will be based on the Safety Population as defined in Section 6.2.2. Patients will be grouped according to treatment received in Cycle 1.

#### 6.2.14.1. Extent of Exposure

For Abemaciclib, extent of exposure will be measured by pill counts and summarized by cycle and cumulatively. The summary will include total dosage taken and dose intensity. Dose intensity will be calculated as the ratio of total dose taken to the assigned cumulative dose. The assigned cumulative dose for each patient during each cycle is 200 mg per dose  $\times$  2 doses per day  $\times$  28 days = 11200 mg. The assigned cumulative dose while on study is 11200 mg  $\times$  number of cycles started.

For erlotinib, exposure will be measured in a similar approach. The assigned cumulative dose for each patient during each cycle is 150 mg per day  $\times$  28 days = 4200 mg. The assigned cumulative dose while on study is 4200 mg  $\times$  number of cycles started.

Dose adjustments and omissions, along with the reason for adjustment or omission, will be summarized for Abemaciclib and erlotinib.

#### 6.2.14.2. Adverse Events

Verbatim text for the adverse events (AEs) will be entered by the investigator, as well as the AE terms and severity grades per CTCAE Version 4.0. In addition, AE verbatim text will also be mapped by the sponsor or designee to corresponding terminology within MedDRA.

Since all the terms in CTCAE Version 4.0 are themselves LLTs of MedDRA, adverse events will be handled in the following manner:

- The CTCAE Version 4 term reported by the investigator will be mapped to the corresponding MedDRA PT and system organ class (SOC), unless the reported CTCAE term is 'Other specify'.
- If the reported CTCAE term is 'Other specify' the MedDRA LLT, PT and SOC mapped from the verbatim AE term will be used.
- Preferred terms identified by Medical as clinically identical or synonymous will be grouped together under a single consolidated term. For example, 'Asthenia' and 'Fatigue' will be reported as 'Fatigue.' See Appendix 1 for a complete listing. This listing may be updated prior to database lock as new synonymous terms are observed.
- Additional listings and summaries will use the PT resulting from this process.

Serious adverse event (SAE) and relationship of AE to the study drug are defined in protocol section 10.3.1. A treatment emergent adverse event (TEAE) is defined as any AE that begins between the day of first dose and thirty days after treatment discontinuation (or up to any time if serious and related to study treatment), or any pre-existing condition that increases in CTCAE grade between the day of first dose and thirty days after treatment discontinuation (or up to any time if serious and related to study treatment).

The following TEAE/SAE listings and summaries will be produced:

- Overview of TEAEs
- Summary of TEAEs by PT (all grade and grade  $\geq$  3)
- Summary of TEAEs by SOC and PT (all grade and grade  $\geq$  3)
- Summary of TEAEs by PT and maximum grade (1-5)
- List of SAEs
- Summary of SAEs by SOC and PT (all grade and grade  $\geq$  3)

The four summaries will be produced for all TEAEs/SAEs and repeated for TEAEs/SAEs related to study treatment.

In addition, summaries will be produced for TEAEs as a reason for study treatment discontinuation, dose adjustment/withholding or hospitalization by SOC and PT.

#### 6.2.14.3. Deaths

All deaths on study not attributed to study disease by the investigator will be listed along with the reason for death, if known. For those deaths attributed to an AE, the listing will include the PT of the AE. A summary of deaths including reasons for death will be produced.

#### 6.2.14.4. Clinical Laboratory Evaluation

All relevant hematology and chemistry laboratory values will be graded according to CTCAE Version 4. These calculated grades will be summarized by cycle and maximum post-baseline grade over the entire study.

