  - hematologic: absolute neutrophil count (ANC) ≥1.5 × 10^9/L, platelets ≥100 × 10^9/L, and hemoglobin ≥8 g/dL. Patients may receive erythrocyte transfusions to achieve this hemoglobin level at the discretion of the investigator. Initial treatment must not begin until the day after the erythrocyte transfusion.
  - hepatic: bilirubin ≤1.5 × the upper limit of normal (ULN), alanine aminotransferase (ALT) and aspartate transaminase (AST) ≤3.0 times ULN. For patients with hepatic metastases, ALT and AST equaling ≤5.0 times ULN are acceptable.
  - renal: serum creatinine  $\leq 1.5 \times ULN$
- [10] are  $\geq 18$  years of age
- [11a] are a man and agree to use a reliable method of birth control and to not donate sperm during the study and for at least 3 months following the last dose of study drug(s) or country requirements, whichever is longer, OR
- [11b] are a woman of child-bearing potential who tests negative for pregnancy at the time of enrollment based on a serum pregnancy test and agrees to use a reliable method of birth control during the study and for 3 months following the last dose of the study drug(s) or country requirements, whichever is longer
- [12] have an estimated life expectancy of at least 12 weeks
- [13] have given written informed consent/assent prior to any study-specific procedures
- [14] are able to swallow oral medications
- [15] are reliable and are willing to follow study procedures

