### 10.3.1. Adverse Events

Lilly has standards for reporting AEs that are to be followed regardless of applicable regulatory requirements that may be less stringent. A clinical study AE is any untoward medical event associated with the use of a drug in humans, whether or not it is considered related to that drug.

Lack of drug effect is not an AE in clinical trials, because the purpose of the clinical trial is to establish drug effect.

Any clinically significant findings from electrocardiograms (ECGs; for example, QTc prolongation), labs, vital sign measurements, other procedures, and so on that result in a diagnosis should be reported to Lilly or its designee. All non-clinically significant findings must be documented in the patient record as not clinically significant and therefore will not be documented in the eCRF.

Cases of pregnancy that occur during maternal or paternal exposures to study drug should be reported. Data on fetal outcome and breast-feeding are collected for regulatory reporting and drug safety evaluation.

Study site personnel will record the occurrence and nature of each patient's preexisting conditions, including clinically significant signs and symptoms of the disease under treatment in the study. All non-clinically significant findings must be documented in the patient record as not clinically significant and therefore will not be documented in the eCRF.

After the study ICF is signed, site personnel will record the occurrence and nature of any AEs and any change in the preexisting condition(s). All AEs related to protocol procedures are reported to Lilly or its designee.

In addition, all AEs occurring after the patient receives the first dose of study drug must be reported to Lilly or its designee via eCRF.

Investigators will be instructed to report to Lilly or its designee their assessment of the potential relatedness of each AE to protocol procedure or study drug via eCRF.

The investigator will decide whether he or she interprets the observed AEs as related to disease, to the study drug, study procedure, or other concomitant treatment or pathologies. To assess the relationship of the AE to the study drug or procedure, the following terminologies are defined:

- **Probably related**: a direct cause and effect relationship between the study treatment and the AE is likely

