# 10.3.3. Safety Monitoring

The Lilly CRP will monitor safety data throughout the course of the study.

Lilly will review SAEs within time frames mandated by company procedures. The Lilly CRP will, as is appropriate, consult with the functionally independent GPS therapeutic area physician or clinical scientist, and review:

- trends in safety data
- laboratory analytes
- adverse events
- If a patient experiences elevated ALT  $>5 \times$  ULN and elevated total bilirubin  $>2 \times$  ULN, clinical and laboratory monitoring should be initiated by the investigator.
- Details for hepatic monitoring depend upon the severity and persistence of observed laboratory test abnormalities. To ensure patient safety and comply with regulatory guidance, the investigator is to consult with the Lilly CRP regarding collection of specific recommended clinical information and follow-up laboratory tests (see Attachment 3).

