## 6.2.3. Definitions and Conventions

Study drug refers to Abemaciclib or erlotinib.

**Study treatment** refers to Abemaciclib + best supportive care or erlotinib + best supportive care.

The **date of randomization** is the date the patient was randomly assigned to Abemaciclib + best supportive care or erlotinib + best supportive care using the interactive web response system (IWRS).

The date of first dose is the date of the first dose of study drug.

The **baseline value of a safety assessment** is the last value observed prior to the first dose of study drug.

The **baseline value of an efficacy assessment** is the last value observed prior to the date of randomization. If a patient's first assessment occurs after randomization but prior to the first dose, this assessment will be used as the baseline.

The study day of a safety event or assessment will be calculated as:

- the difference between the date of the event or assessment and the date of first dose plus 1 for all events or assessments occurring on or after the day of first dose. For example, if an event occurs on 08JUN2014 and the date of first dose was 06JUN2014, the study day of the event is 3.
- the difference between the date of the event or assessment and the date of first dose for all events or assessments occurring before the day of first dose. For example, if an event occurs on 05JUN2014 and the date of first dose was 06JUN2014, the study day of the event is -1.

The study day of an efficacy event or assessment will be calculated as:

- the difference between the date of the event or assessment and the date of randomization plus 1 for all events or assessments occurring on or after the date of randomization.
- the difference between the date of the event or assessment and the date of randomization for all events or assessments occurring before the date of randomization.

One **month** is defined as 365/12 days.

Unless otherwise noted, **summaries of continuous variables** will include a mean, median, standard deviation, minimum, and maximum.

Unless otherwise noted, **summaries of categorical variables** will include the frequency and percentage (relative to the population being analyzed) of each category.

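### The SAP's table of worst post-baseline laboratory grades ignores baseline, so graded abnormalities present at entry that never worsen are counted in it

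*SAP*

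**What the plan says.** **The laboratory table.** SAP 6.2.14.4 grades the relevant hematology and chemistry values by CTCAE. It then states: "These calculated grades will be summarized by cycle and maximum post-baseline grade over the entire study". The section asks for no shift from baseline and does not restrict counting to patients whose grade rose.

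**The baseline that exists.** SAP 6.2.3 defines the baseline of a safety assessment, which "is the last value observed prior to the first dose of study drug". The laboratory section does not refer to it.

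**Who may enter.** Protocol 7.1, criterion [9], sets the liver limits as "hepatic: bilirubin ≤1.5 × the upper limit of normal (ULN), alanine aminotransferase (ALT) and aspartate transaminase (AST) ≤3.0 times ULN", and adds: "For patients with hepatic metastases, ALT and AST equaling ≤5.0 times ULN are acceptable". The renal line ("renal: serum creatinine") has a limit of 1.5 × ULN. Hemoglobin may be as low as 8 g/dL, and transfusion to reach that level is allowed.

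**The adverse-event rule.** SAP 6.2.14.2 treats an event already present at entry differently. It is treatment-emergent only if it is "any pre-existing condition that increases in CTCAE grade between the day of first dose and thirty days after treatment discontinuation" (or later, if serious and related). Protocol 12.2.12 likewise compares on-treatment events with pre-existing conditions. It also plans separate summaries of laboratory-based treatment-emergent adverse events (TEAEs) by maximum grade. The list of outputs in SAP 6.2.14.2 does not name those separate summaries.

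**The concern.** The SAP applies two standards to the same kind of finding. In the adverse-event tables, an entry abnormality counts only if its grade rises. In the laboratory table, it counts if it is merely still there. The eligibility limits admit values outside the normal range for several analytes, so some patients can enter with a grade and carry it through unchanged.

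At stake is how the calculated laboratory grades are read. Protocol 9.4.1 names anemia and increased blood creatinine among the common events possibly related to abemaciclib, and hemoglobin and creatinine are two of the analytes for which abnormal entry values are allowed. From the worst-grade table alone, a reader cannot tell what arose on treatment from what was present before it.

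**Working it through.** The plan gives no figure for laboratory grades or for how many patients are abnormal at entry, so there is no stated number to reproduce. The rates below are assumptions that show the mechanism.

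**Notation**
- b: share of each arm with a grade of 1 or more at entry, taken as equal in the two arms because of randomization. Each such patient is assumed to be seen at that grade or higher at least once after baseline.
- t: probability of a new abnormality among patients normal at entry.
- w: probability that a patient abnormal at entry rises to a higher grade.
- Subscripts A and E denote abemaciclib and erlotinib.

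**Formulas for the any-grade rate, whole arm as denominator**
- Table as planned: b + (1 − b)t
- Emergent (worst grade above baseline grade): (1 − b)t + bw
- Difference between arms, as planned: (1 − b)(t_A − t_E)
- Difference between arms, emergent: (1 − b)(t_A − t_E) + b(w_A − w_E)

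The planned any-grade table therefore loses the term b(w_A − w_E) and nothing else from the difference. The ratio is affected even when that term is zero, because b is added to both arms.

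**Case 1: no one abnormal at entry worsens (w = 0), with t = 50% versus 20%**

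| b | Emergent A vs E | Difference | Ratio | Planned table A vs E | Difference | Ratio |
|---|---|---|---|---|---|---|
| 20% | 0.8 × 50% = 40% vs 0.8 × 20% = 16% | 24 points | 2.5 | 60% vs 36% | 24 points | 1.67 |
| 40% | 0.6 × 50% = 30% vs 0.6 × 20% = 12% | 18 points | 2.5 | 70% vs 52% | 18 points | 1.35 |

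At b = 40%, unchanged entry abnormality makes up 40/70 = 57% of the abemaciclib count and 40/52 = 77% of the erlotinib count. With the planned arm sizes of 270 and 180, that is 108 and 72 patients.

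**Case 2: patients abnormal at entry worsen at the same rate as others become abnormal (w = t), with t = 30% versus 15%**

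The emergent rates are then 30% versus 15% (difference 15 points, ratio 2.00) at every b.

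| b | Planned table A vs E | Difference | Ratio | Unchanged share of A count, b(1 − t_A)/rate |
|---|---|---|---|---|
| 10% | 37.0% vs 23.5% | 13.5 points | 1.57 | 19% |
| 30% | 51.0% vs 40.5% | 10.5 points | 1.26 | 41% |
| 50% | 65.0% vs 57.5% | 7.5 points | 1.13 | 54% |

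Here the absolute difference does shrink, by b(w_A − w_E): 1.5, 4.5 and 7.5 points.

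**Reading the two cases together.** Inflated absolute rates and a smaller ratio appear in both. A smaller absolute difference appears only in Case 2, where worsening among patients abnormal at entry is more frequent on abemaciclib.

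**The case against.** **Laboratory toxicity is already reported against baseline elsewhere.** This is correct as far as it goes. The TEAE rule in SAP 6.2.14.2 and the laboratory-based TEAE summaries in Protocol 12.2.12 both exclude an unchanged pre-existing condition. A reader might infer that all laboratory toxicity in this plan ignores baseline. The documents do not support that, and the point is confined to one table.

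**The adverse-event tables capture bare laboratory findings.** Protocol 10.3.1 says that clinically significant findings from "labs, vital sign measurements, other procedures, and so on that result in a diagnosis should be reported". A reader might infer that a laboratory change reaches the adverse-event tables only through a diagnosis. That goes too far: the protocol's definition of an adverse event includes an abnormal laboratory finding, and SAP Appendix 1 consolidates terms such as decreased hemoglobin and decreased neutrophil count. What remains is that these tables depend on an investigator judging a finding significant and reporting it. The same section keeps findings judged not clinically significant out of the eCRF, and site staff know the treatment. The calculated grades do not depend on that judgement, so they are the fuller record.

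**A by-cycle summary may include baseline.** The study schedule has a baseline entry in its cycle row, with hematology and chemistry drawn then. A baseline column is therefore possible. It would show the proportion abnormal before treatment, but not which patients changed.

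**The difference between arms is not shown to shrink.** This stands where patients abnormal at entry do not worsen, as in Case 1. If they do worsen, their new grade appears in the maximum-grade distribution, though mixed with patients who started at that grade.

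**The combined liver criterion has no table.** A reader might infer that the plan also omits a required analysis of ALT above 5 × ULN together with bilirubin above 2 × ULN. Protocol 10.3.3 uses that combination to say that "clinical and laboratory monitoring should be initiated by the investigator". It is a monitoring trigger, not a planned endpoint, and it forms no part of this point.

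**Conclusion.** The point holds for the worst-grade table in SAP 6.2.14.4. As written, a graded entry abnormality that persists unchanged is counted there, contrary to the worsening principle that the SAP applies to adverse events. Absolute any-grade rates are inflated in both arms and the ratio between arms is pulled toward 1. In the illustration with 40% abnormal at entry and no worsening among them, a ratio of 2.5 is shown as 1.35.

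The size rests on assumed values of b, t and w, on equal entry prevalence in the two arms, and on entry abnormalities persisting. It also assumes that some of the admitted values carry a CTCAE grade. The documents reproduce the grading criteria only for diarrhea, so nothing can be said about any particular grade, including Grade 3 or higher.

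A reader might infer that the table favors one arm or always hides part of the absolute difference. Neither follows. Randomization balances entry grades in expectation, and the difference shrinks only under unequal worsening among patients abnormal at entry.

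The consequence is modest. The table is descriptive, there are no prespecified safety stopping rules that it could feed, and the overall survival analysis is unaffected. It is still worth correcting, because the adverse-event tables mitigate it only in part and the SAP omits the separate laboratory-based TEAE summaries that the protocol plans.

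**What to change.** In SAP 6.2.14.4, add two outputs by arm:

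1. **Treatment-emergent laboratory grades.** Count a patient only if the maximum post-baseline grade is higher than the grade at the SAP 6.2.3 safety baseline.
2. **A shift table from baseline grade to worst post-baseline grade** for each analyte. Include a row for a missing baseline grade, since SAP 6.2.4 does not impute missing values.

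State that the rule follows the TEAE definition in SAP 6.2.14.2, and bring the SAP output list into line with the laboratory-based TEAE summaries in Protocol 12.2.12. The existing worst-grade table can stay beside these.

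The cost is SAP wording and one or two tables. Hematology and chemistry are already collected in both arms at baseline, at each cycle and at the 30-day follow-up visit (Protocol Attachment 1), so nothing is added for sites or patients. SAP 6.2.1 allows a clarification of this kind before the aggregate database is unblinded.

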#### 6.2.14.5. Vital Signs and Other Physical Findings

Temperature, blood pressure, pulse rate, respiration rate, weight and ECOG PS will be summarized by cycle.

#### 6.2.14.6. Electrocardiograms

Local electrocardiograms (ECGs) will be summarized by cycle and overall. The summary by cycle will classify patients as having normal or abnormal ECG and summarize AEs identified by ECG within each cycle. The overall summary will classify patients as having an abnormal ECG at any point and summarize all AEs identified by ECG.

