# 10.3.2. Other Safety Measures

### 10.3.2.1. Electrocardiograms

For each patient receiving abemaciclib, 12-lead digital ECGs will be collected according to the Study Schedule (Attachment 1) and Table JPBK.10.2 as single ECGs. For each patient receiving erlotinib, an ECG will be collected at baseline only. Patients must be supine for approximately 5 to 10 minutes before ECG collection and remain supine but awake during ECG collection.

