#### Table JPBK.10.2. Schedule for Electrocardiogram Collection

Electrocardiogram	Cycle and Day	Timing
1	Baseline	≤14 Days
2	Cycle 1 Day 1	Predose a
3	Cycle 1 Day 1	4 to 6 hours postdose
4	Cycle 2 Day 1	4 to 6 hours postdose
5	Cycle 7 Day 1	4 to 6 hours postdose
6	Visit 801	30 days after study drug discontinuation

Abbreviations: C1D1 = Cycle 1 Day 1; ECG = electrocardiogram.

a If baseline ECG performed with 24 hours of C1D1 predose ECG, the C1D1 predose ECG may be omitted.

Electrocardiograms may be obtained at additional times, when deemed clinically necessary. Collection of more ECGs than expected at a particular time point is allowed when needed to ensure high-quality records.

Electrocardiograms will be interpreted by a qualified physician (the investigator or qualified designee) at the site as soon after the time of ECG collection as possible, and ideally while the patient is still present, to determine whether the patient meets entry criteria and for immediate patient management, should any clinically relevant findings be identified.

After enrollment, if a clinically significant increase in the QT/QTc interval from baseline, or other clinically significant quantitative or qualitative change from baseline, is present, the investigator will assess the patient for symptoms (for example, palpitations, near syncope, or syncope) and to determine if the patient can continue in the study. The investigator or qualified designee is responsible for determining if any change in patient management is needed and must document his/her review of the ECG printed at the time of evaluation.

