- h Data on SAEs that occur before the end of trial will be stored in the collection database and the Lilly Safety System. During long-term follow-up, only SAEs that are related to protocol procedures or study drug will be collected. All drug- or procedure-related adverse events and serious adverse events should be followed until they resolve, are no longer considered to be drug- or procedure-related, become stable or return to baseline, the patient starts a new therapy, the patient dies, or the patient becomes lost to follow-up. Frequency of evaluation is left to the judgment of the investigator.
- Laboratory assessments should occur on Day 1 (±3 days) of each cycle and Day 15 (± 3 days) of Cycles 1 and 2. If the baseline laboratory assessment was conducted ≤3 days prior to Cycle 1 Day 1, reassessment is not required at Cycle 1 Day 1. For central versus local labs, refer to Attachment 2.
- j Perform pregnancy tests for woman of child-bearing potential.
- k Perform pregnancy tests once every 28 days (±7 days) prior to administration of study drug, where required by local regulations.
-  Sparse PK samples will be collected on Cycle 1 Day 1, Cycle 2 Day 1 and Cycle 3 Day 1 (only for patients receiving abemaciclib).
- m A plasma sample should be collected at baseline at the time FFPE tissue is requested for testing at the Study JPBK central laboratory. Patients who enter the study with a local KRAS test result may omit this baseline sample. Patients that have submitted FFPE tissue during pre-screening may have this baseline sample collected at the time of other blood laboratory samples. Additional samples are collected on all randomized patients at Cycle 1 Day 1 and Cycle 2 Day 1.
- n Local ECG (no replicates required).
- A baseline ECG will be collected from all patients.
- P ECG will be collected from patients receiving abemaciclib only. Two ECG will be collected on Cycle 1 Day 1. The first ECG will be collected predose; the second will be collected 4 to 6 hours postdose. If the patient had a baseline ECG performed within 24 hours of the predose ECG at Cycle 1 Day 1, the scheduled predose ECG may be omitted.
- 9 ECG will be collected from patients receiving abemaciclib only. An ECG will be collected 4 to 6 hours postdose on Cycle 2 Day 1.
- r If the patient received abemaciclib for 6 months, an additional ECG will be collected 4 to 6 hours postdose Cycle 7 Day 1.

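### The overall ECG summary counts an abnormal tracing at any time, but only abemaciclib patients have scheduled ECGs after dosing, so the two columns are not comparable

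*SAP*

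**What the plan says.** SAP 6.2.14.6 opens with "Local electrocardiograms (ECGs) will be summarized by cycle and overall". The by-cycle part labels each patient normal or abnormal within the cycle. For the other part, "The overall summary will classify patients as having an abnormal ECG at any point", together with a summary of adverse events found by ECG. The section does not mention baseline, arm or denominator. SAP 6.2.14, which governs all safety output, adds: "Patients will be grouped according to treatment received in Cycle 1".

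The protocol gives the arms different schedules. Section 10.3.2.1 states: "For each patient receiving erlotinib, an ECG will be collected at baseline only". The Attachment 1 footnotes agree. At baseline, "A baseline ECG will be collected from all patients"; after that, "ECG will be collected from patients receiving abemaciclib only. Two ECG will be collected on Cycle 1 Day 1", and the Cycle 2 and Visit 801 footnotes carry the same restriction to abemaciclib. Cycle 7 has its own condition: "If the patient received abemaciclib for 6 months, an additional ECG will be collected 4 to 6 hours postdose Cycle 7 Day 1". In Table JPBK.10.2 the last listed tracing, at Visit 801, is timed "30 days after study drug discontinuation". The text below that table also allows extra ECGs when clinically needed, without naming an arm.

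**The concern.** One label covers two different quantities. On erlotinib it is mainly the share of patients whose single baseline tracing was abnormal. On abemaciclib it is the share with at least one abnormal tracing among several. More tracings give more chances of an abnormal one, so the abemaciclib column is expected to be higher even if the drug does nothing to the heart. A patient already abnormal at entry is also counted in the same way as one who became abnormal on treatment.

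The by-cycle part has a related gap, because erlotinib has no scheduled ECG in any cycle. The summary of adverse events found by ECG shares the problem: Protocol 10.3.1 asks for ECG findings that lead to a diagnosis to be reported, and scheduled tracings find more of them.

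The stake is interpretation. Protocol 7.2.1 says the effect of abemaciclib on QTc is not known, so ECG output will be read with interest. SAP 6.2.15 also permits further subgroup analyses if safety results show important imbalance between arms.

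**Working it through.** **Counting tracings.** Table JPBK.10.2 lists six for abemaciclib: baseline, Cycle 1 Day 1 predose, Cycle 1 Day 1 postdose, Cycle 2 Day 1, Cycle 7 Day 1 and Visit 801.

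- Stopping before Cycle 7 removes one: 6 − 1 = 5.
- The predose tracing may be skipped if the baseline one was within 24 hours: 5 − 1 = 4. Missed visits reduce this further.
- SAP 6.2.3 defines the safety baseline as the last value before first dose. The predose tracing, when done, is therefore itself the baseline value. Scheduled tracings after dosing number at most 6 − 2 = 4.
- Erlotinib has one scheduled tracing, and none after dosing.

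**Expected result with no drug effect.** The plan states no expected ECG figure, so there is none to reproduce. Two inputs are assumptions: *p*, the chance that any one tracing is abnormal, and *ρ*, the correlation between tracings in the same patient. With *k* tracings:

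- Independent tracings (*ρ* = 0): P(at least one abnormal) = 1 − (1 − p)^k. At p = 10%: 1 − 0.9^4 = 34.4%; 1 − 0.9^6 = 46.9%.
- Correlated tracings (beta-binomial): set a = p(1 − ρ)/ρ and b = (1 − p)(1 − ρ)/ρ. P(none abnormal) is the product of (b + i)/(a + b + i) for i = 0 to k − 1. At p = 10% and ρ = 0.5, a = 0.1 and b = 0.9, and for k = 4 the product is (0.9/1)(1.9/2)(2.9/3)(3.9/4) = 0.806, so 19.4% have at least one abnormal tracing.
- ρ = 1: the answer is p for every k, and the excess is zero.

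The table assumes that erlotinib has its one scheduled tracing only. Abemaciclib entries are for 4 / 6 tracings.

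| p per tracing | Erlotinib | Abemaciclib, ρ = 0.9 | Abemaciclib, ρ = 0.5 | Abemaciclib, independent |
|---|---|---|---|---|
| 5% | 5% | 5.9% / 6.1% | 10.1% / 11.7% | 18.5% / 26.5% |
| 10% | 10% | 11.7% / 12.1% | 19.4% / 22.3% | 34.4% / 46.9% |
| 20% | 20% | 23.0% / 23.7% | 36.2% / 40.8% | 59.0% / 73.8% |

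At p = 10% the excess runs from about 2 percentage points (11.7 − 10 = 1.7; 12.1 − 10 = 2.1) at ρ = 0.9, through 9 to 12 points at ρ = 0.5, to 24 to 37 points under independence.

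**If baseline is meant to be excluded.** Erlotinib then contributes no scheduled tracing. Abemaciclib, with 3 / 4 post-dose tracings at p = 10%, gives 11.4% / 11.7% at ρ = 0.9 and 17.4% / 19.4% at ρ = 0.5. The erlotinib column would hold only clinically triggered ECGs.

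**Comparison with the rest of the SAP.** Laboratory values (6.2.14.4) are summarized by maximum post-baseline grade. Adverse events (6.2.14.2) count a pre-existing condition only if its grade rises. The ECG section sets neither limit.

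**The case against.** The section is descriptive. It plans no ECG test and does not itself ask for a display by arm, although SAP 6.2.14.7, the section that follows it, does. The unequal schedule is stated openly in the protocol, so an informed reader could allow for it. This stands as a limit on the consequences. But the grouping rule in SAP 6.2.14 makes a two-column table the natural output, and nothing in the SAP requires a caveat on it.

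It can also be said that the wording is silent on baseline and may mean on-study tracings only. The silence is real, but that reading does not help, because erlotinib would then have no scheduled ECG to summarize.

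Some stronger readings are tempting and are not supported:

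- A reader might infer that the erlotinib figure is purely baseline prevalence. Clinically triggered ECGs are allowed in either arm. They may narrow the gap, but symptom-driven tracings do not equalize detection.
- A reader might take six as the usual abemaciclib count. It is a ceiling.
- A reader might take the 34% to 47% figures as the likely size. They need independent tracings within a patient, some possibly on the same day, and any lasting abnormality breaks that.
- A reader might infer that the QTc question rests on this table. It is a normal/abnormal classification. Under Protocol 10.3.2.1 the investigator assesses clinically significant QT/QTc increases patient by patient, and ECG findings that lead to a diagnosis also reach the adverse event tables.

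**Conclusion.** The point holds as a bias of known direction and unknown size in a descriptive safety table. With no drug effect and few unscheduled erlotinib tracings, the overall summary is expected to show more abnormality on abemaciclib unless every tracing in a patient reads the same. It also leaves pre-existing and new abnormalities mixed. The direction follows from the schedules and the wording. The size depends on a per-tracing rate and a within-patient correlation that the documents do not give; at an assumed 10% it runs from about 2 points when tracings are highly correlated to 37 points at the independent extreme. The documents do not support a claim that a false ECG signal will be declared, since no ECG test is planned. OS, PFS and ORR are not affected, and the matter is minor.

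**What to change.** Revise SAP 6.2.14.6 and its table shell as follows:

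- Show baseline ECG status for both arms, using the safety baseline of SAP 6.2.3. This compares one baseline value per patient in each arm, so the expected difference with no effect is zero.
- For abemaciclib only, report post-baseline results as shift from baseline and as treatment-emergent abnormality (normal at baseline, abnormal later). Use the number of patients with an ECG at each visit as the denominator.
- List unscheduled erlotinib ECGs separately, so that they are not lost.
- Footnote the unequal schedule on any two-arm ECG table and on any summary of adverse events found by ECG.

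This needs no added ECGs and no change to data collection. The small cost is that no between-arm contrast of post-baseline ECGs is shown, but the schedule does not support one.
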